The IY-ASLD® intervention has recently been piloted within the Spanish Mental Health system (Valencia 2021). Due to the COVID-19 pandemic, the program was piloted in an online format, including all the elements of the face-to-face intervention with families and therapist connected online. Preliminary results showed that parental compliance and satisfaction with the intervention was very high (Villalta in press), and several advantages of the online format were highlighted (such as better family logistics and improved access to therapy). In view of these results, and taking into account that families of infants with genetic abnormalities are scattered all over the territory, we aim to examine the feasibility and initial effectiveness of delivering the IY-ASLD® intervention in an online format in spite of the pandemic context. It is also of note that support groups are an important resource for many families living with children with rare diseases, and it has been described that meeting via teleconference is a facilitating factor.

AIMS AND HYPOTHESIS

The main aim of the present study is to examine the feasibility and initial effectiveness of the IY-ASLD® intervention for parents of children with developmental difficulties of a genetic basis. We specifically aim to describe the compliance and satisfaction of these parents with the program, from a quantitative and qualitative perspective, and provide initial evidence on its effectiveness in terms of improving parental distress, parenting skills, as well as overall mental health difficulties in their children.

In order to achieve these goals, we designed a controlled randomized pragmatic trial where families will be randomly allocated to the intervention group (receiving the IY-ASLD® intervention online) or to the treatment as usual condition (TAU). We recruited children from the three pediatric hospitals that have a specialized unit in genetic diseases and in child mental health.

The research hypotheses are as follows:

- I. Parents' compliance with the program is acceptable (attending at least 15 of the 22 online sessions and a minimum of 50% of parents finishing the intervention).
- II. Parents report acceptable levels of satisfaction with the program.
- III. Parents who received the intervention present reduced levels of parental stress when compared to the control group.
- IV. Parents who received the intervention show reduced levels of depressive symptoms and expressed

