Parents will be recruited from the three specialist units in paediatric genetic abnormalities within the three Hospitals. A leaflet with the inclusion and exclusion criteria will be handed out to clinicians working in the services. Clinicians will discuss the study with eligible families and will ask the families permission to be contacted by the study researchers. If they agree to be contacted about the project, a research assistant will call the family to discuss the study further. If the family is interested in participating in the study the researcher will set up an appointment to evaluate all the inclusion criteria (including the Autism Diagnostic Observation Schedule-ADOS-). During this visit, researchers will make sure that participants receive all the necessary information and have the opportunity to ask any questions. If participants meet the inclusion criteria, parents will be asked to sign the informed consent and to complete the pre-intervention assessment. Any children excluded from the study due to scoring above diagnostic cut-off for ASD (ADOS) will be referred to specialised assessment within the mental health public system. Participants will be able to discontinue the treatment sessions or drop out from the control group at any point at their request. The participation in the study will not affect their usual treatment.

Randomization:

Randomization will take place once all the participating families have completed baseline measures. They will be randomly allocated to the intervention group or to the TAU condition. An independent researcher will carry out the randomization process, and researchers who are responsible for patient recruitment or intervention delivery will not be involved. Due to the pragmatic and clinically focused nature of the study, further blinding procedures will not be possible.

Intervention:

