- Parenting skills will be assessed with the Alabama Parenting Questionnaire-Preschool revision (APQ-Pr). The APQ-Pr is a 32-item parent-reported questionnaire measuring parenting practices that are consistently associated with disruptive child behaviors. This version has 3 dimensions: positive parenting, inconsistent parenting, and punitive parenting. It will be collected before and after the intervention. This measure has shown good internal consistency and validity.
- Parental-expressed emotions will be evaluated with the Autism-Specific Five Minute Speech Sample (ASFMFSS). This is a narrative 5-min interview used to measure parental-expressed emotions for children with ASD and related disorders. Parents are asked to speak about their child and the parent-child relationship —“I'd like you to speak for 5 minutes, telling me what kind of person (child name) is and how the two of you have got along together over the past 6 months.” Speech samples are audiotaped, transcribed, and coded following four global categories: (a) initial statement, (b) warmth, (c) relationship, (d) emotional over-involvement, (e) critical comments, and (f) positive comments. Expressed emotions will be measured before and after the intervention. Benson et al. [49] assessed 30 randomly selected speech samples by three different raters. Inter-rater reliability and code-recode reliability on two separate occasions, for all six AS-FMSS components and for total EE score, were both in the good to excellent range.
- Semi-structured individual interviews will be conducted after the last session of the intervention to qualitatively explore: (1) parents' perceived changes in their parenting skills and distress, and (2) clinicians' experiences with the intervention delivered.

Data collection:

Quantitative data collection:

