Data will be collected at baseline (before performing randomization) and after finishing the IY-ASLD® intervention. Parents consenting to participate will be offered a hospital appointment before the intervention with a research assistant to evaluate inclusion criteria (parental questionnaires and ADOS). If they meet inclusion criteria they will then be contacted on the phone to complete the baseline assessment (including self-report measures, children outcome measures, and a voice recording for the ASFMSS tool). If both parents participate in the study, they will fill out the children's outcome measures together (by consensus) and the parental outcome measures individually.

Qualitative data collection:

Qualitative data will be collected at baseline (focus groups) and after finishing the IY-ASLD® intervention (interviews). Parents included in the study will be contacted on the phone to be invited to participate in an online focus group. We will aim for a representative sample in terms of children's diagnosis, age, gender

and cognitive status (according to DP-3 cognitive subscale score). If a parent declines to participate in a focus group, another parent will be contacted until 6 individuals per focus group are recruited. The focus groups will be delivered online and will be conducted by a psychologist trained in qualitative methods, external to the clinical team, and they will be audio-recorded and transcribed verbatim.

The same psychologist will conduct the individual interviews to parents and clinicians, which will have an online format and will be audio-recorded and transcribed verbatim.

SCIENTIFIC AND SOCIAL INTEREST

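### The statement that no further blinding is possible is too broad: read literally, it rules out masked coding of the recorded speech samples, the only rater-scored outcome compared between arms

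*Protocol*

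**What the plan says.** The Protocol's section on Randomization sets the order of events: "Randomization will take place once all the participating families have completed baseline measures". Someone independent of the study team then allocates families, and those who recruit or deliver the intervention take no part. The section closes with: "Due to the pragmatic and clinically focused nature of the study, further blinding procedures will not be possible". No role and no outcome is exempted.

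Hypothesis IV in Aims and Hypothesis is a comparison with the control group: "Parents who received the intervention show reduced levels of depressive symptoms and expressed" emotions. The Outcomes section lists expressed emotion among the secondary outcomes and describes how the AS-FMSS is scored: "Speech samples are audiotaped, transcribed, and coded following four global categories". On timing it says: "Expressed emotions will be measured before and after the intervention".

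Under Quantitative data collection, the baseline assessment is described as "including self-report measures, children outcome measures, and a voice recording for the ASFMSS tool", so the recording is listed apart from the self-report measures. If both parents take part, they complete the child measures jointly "and the parental outcome measures individually".

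The Protocol does not say who codes the speech samples, or whether coders will know the arm or the time point.

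**The concern.** The reason given for the lack of blinding is the pragmatic, clinical character of the trial. That covers parents, who know whether they attended a group, and the clinicians who lead the groups. It does not cover a coder working afterwards from stored material, who has no need to know the arm.

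Coding warmth, relationship or critical comments calls for judgement, and a coder who knows which families had the programme may score in the expected direction. That is detection bias in a between-arm comparison. A study team that followed the sentence as written would have no reason to guard against it. This goes beyond a detail left open for a later document, because the Protocol positively states that masking cannot be done.

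**Working it through.** The Protocol gives no figure on this point; its sample-size calculation concerns parental stress and does not enter here. The check is a classification of the outcomes, followed by simple counts.

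**1. Who scores each effect measure collected before and after the intervention**

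| Measure | Section of the Protocol | Scored by | Can scoring be masked? |
|---|---|---|---|
| PSI-SF (parental stress) | Outcomes | Parent | No |
| BDI (depressive symptoms) | Outcomes | Parent | No |
| APQ-Pr (parenting skills) | Outcomes | Parent | No |
| CBCL 1.5-5 (child symptoms, Hypothesis VI) | Measures, baseline descriptors | Parent | No |
| AS-FMSS (expressed emotion) | Outcomes | Rater, from a recording | Yes |

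Rater-scored: 1 of 5. The CBCL 1.5-5 sits among the baseline descriptors but is collected at both time points.

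Three other elements drop out:
- The ADOS-2 is also rater-scored, but it serves eligibility before randomization.
- The interviews after the intervention involve intervention-arm parents and clinicians only, so they give no between-arm comparison.
- Attendance and satisfaction concern the intervention arm only.

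**2. Does the stated reason reach the coders?** The Outcomes section makes coding a separate step after recording and transcription. Nothing in a pragmatic design requires the person doing that step to know the allocation. For this outcome, the claim that blinding is impossible is not supported by the Protocol's own procedure.

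**3. How many samples**

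Inputs: about 68 children (summary at the start of the Protocol), two time points, one or two parents per family, full retention.

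- One parent each: 68 × 2 × 1 = 136.
- Both parents in every family: 68 × 2 × 2 = 272.
- Post-test only: 68 × 1 = 68, up to 68 × 2 = 136.

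The post-test samples are directly exposed. Baseline recordings are made before any allocation exists, so their content cannot reveal the arm; they are exposed only if they are coded after allocation with the arm visible.

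**4. How complete masking can be**

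The prompt asks "how the two of you have got along together over the past 6 months". The online programme has about 22 sessions. Assuming one per week (the Protocol mentions weekly home tasks and weekly calls but gives no session frequency), 22 × 7 = 154 days, and 154 / 30.44 = 5.1 months. This is less than 6 months, so the post-test prompt can span the whole programme, and some parents may mention it.

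**The case against.** The strongest reply is that the sentence was never meant for coders. It closes the Randomization paragraph, straight after a remark about recruiting and delivering staff, and most naturally refers to staff and families. On that reading there is no contradiction, only a loose sentence and silence about who codes. This stands in part: the narrower meaning is possible, and the Protocol nowhere says that coding will be unmasked. But the wording has no exception, and a clarification is needed on either reading.

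The second reply is that little is at stake: one secondary measure, half of one hypothesis out of six, in a trial seeking initial evidence, with recordings that could be coded again later. This is correct, and it limits the importance of the point. Re-coding would, however, repeat work that could be done properly once.

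Third, masking will be imperfect because post-test speech may disclose the programme. This also stands. How many samples would remain masked is unknown, and masking protects only the scoring, not what parents choose to say. Partial masking is still better than none.

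Fourth, the cost may be understated, because the Protocol gives no information about coders or staffing. Coders are needed in any case; the added requirement is that they did not lead groups and cannot see the allocation. That such people are available is an assumption.

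Finally, the unit behind 68 varies: the summary speaks of children, the Sample size section of participants. The counts take 68 as families, following the summary, and are ceilings at full retention.

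**Conclusion.** The concern holds as a point that should be corrected, with medium confidence because the intended scope of the sentence is uncertain. As written, the blinding statement is wider than its reason and gives up protection against coder bias for the one effect measure where the scoring could be protected. The consequence is confined to the expressed-emotion part of Hypothesis IV. The primary feasibility outcomes and the sample size are untouched.

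The sample counts describe how much material is exposed, and the 1-in-5 ratio counts measures; neither is a size of bias. The conclusion depends on the literal reading of the sentence. It does not depend on the weekly-session assumption, which bears only on how complete the masking can be.

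**What to change.** Replace the sentence in the Randomization section with wording such as:

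> Parents and group leaders cannot be blinded. AS-FMSS samples will be labelled with a random ID that carries neither arm nor time point. They will be coded in mixed order, after post-test collection, by study coders who did not deliver the groups and have no access to the allocation list. Coders will record whether a sample revealed the arm.

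If masked coding cannot be arranged, the Protocol should give a reason that is specific to the coders.

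The cost is relabelling the samples, holding the coding until the post-test recordings are in, and choosing coders outside the delivery team. No visit or measure is added. Nothing is removed from the recordings, so no scorable speech is lost; the coders' note on whether the arm was revealed shows how far masking succeeded.

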- emotions when compared to the control group.
- V. Parents who received the intervention present an increase in their positive parenting skills when compared to the control group.
 - VI. Parents who received the intervention report a decrease in the levels of children's externalizing and internalizing symptoms when compared to the control group.

METHODOLOGY

The GAP project will be implemented in three Pediatric Hospitals (Hospital Sant Joan de Déu in Barcelona, Hospital Vall d'Hebron in Barcelona, Hospital Parc Taulí in Sabadell). Participating families will be recruited from specialist paediatric genetic units within each hospital, and will be randomly allocated to the TAU condition or to the intervention group. Clinical psychologists and child psychiatrists working in specialised mental health services for neurodevelopmental disorders within the hospitals will deliver the intervention. Before the intervention takes place, between 4 and 8 focus groups will be carried out with a subsample of families to explore their needs, challenges, preferences and expectations. After the intervention, interviews will be conducted with parents of the intervention group and with clinicians who delivered the intervention.

A mixed-methods approach will be used, considering the benefits of combining quantitative and qualitative methods in health psychology clinical trials (Bishop 2015).

Sample size:

For the sample size calculation, we used the outcome parental stress, measured through the questionnaire Parental Stress Index Short Form (PSI-SF). This is a 36-item scale, with a range of 180 points. There is data showing that a decrease of 16.5 points in the total scale stress score can be seen after attending an IY program. Given that this study will be conducted with parents of children presenting neurodevelopmental difficulties, we anticipated that the decrease in the PSI-SF score would be lower. We estimated the necessary sample size considering a power of 80%, $\alpha = 0.05$, a difference between pre- and post-test of 10 points, and a standard deviation of 20, using a paired-samples t test. We estimated 34 participants needed per arm of the study. Thus, we aim to recruit approximately participants. The drop-out rate has not been included when calculating the sample size, considering that a sample of 68 participants is similar than previous studies and in line with recommendations by the National Institute of Health Research.

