For the focus groups that will be conducted before the intervention, each group will have between 4 and 6 participants (mothers or fathers), considering the recommendations provided by Tausch & Menold (2016). Taking into account potential drop-outs, 6 parents will be contacted per focus group.

For the post-intervention individual interviews with parents, parents will be selected from the 4 intervention groups conducted in the 3 sites: a minimum of 2 parents per group will be interviewed, therefore at least 8 interviews will be conducted. Parents who dropped out of the study will also be invited to participate to explore their experiences. Data saturation will be used to determine the final sample size.

For the post-intervention individual interviews with clinicians, all clinicians that delivered the intervention will be interviewed after the intervention phase.

Eligibility criteria:

The following are the inclusion criteria:

1. Children aged 3.0 – 7.11 years at recruitment
2. Children with a diagnosis or in diagnostic process for high suspicion of a genetic abnormality
3. For children up to 5.11 years with withdrawn (defined as CBCL/1.5-5 scores above the borderline clinical range, T-score > 65) AND/OR pervasive developmental problems (defined as CBCL/1.5-5 scores above the borderline clinical range, T-score > 65) AND/OR socialization difficulties (defined as Vineland-III scores below 1SD in the socialization subdomains).
4. For children over 6 years with social problems (defined as CBCL/6-18 scores above the borderline clinical range, T-score > 65) AND/OR thought problems (defined as CBCL/6-18 scores above the borderline clinical range, T-score > 65) AND/OR socialization difficulties (defined as Vineland-III scores below 1SD in the socialization subdomains).
5. Parents/caregivers showing good understanding of the Spanish or Catalan language
6. Parents/caregivers consenting to take part in the study and signing the informed consent

The following are the exclusion criteria:

1. Children diagnosed with an Autism Spectrum Disorder
2. Children scoring above diagnostic cut-off for Autism or Autism Spectrum Disorder in the ADOS-2.
3. Attending another structured parenting program
4. Children in the care of their local authority

Recruitment:

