The IY-ASLD® program is a 14-session group-based intervention for parents of children presenting neurodevelopmental difficulties. During the COVID-19 pandemic, the Incredible Years developers adapted the intervention to be performed online (22 sessions approximately). Each online group will include approximately 6-10 participants. The intervention includes video modelling and emphasizes the importance of practice-based learning through role-playing. Weekly home tasks will be assigned to parents, and families will be phoned each week to encourage home-based practice. Fidelity to the treatment manual will be ensured in different ways. Group interventions will be conducted by experienced psychiatrists and clinical psychologists, officially trained in the IY-ASLD® model and its online adaptation by an accredited trainer. Group leaders will complete weekly fidelity checklists and will be supervised by certified supervisors throughout the intervention. The TAU condition involves outpatient appointments with neuropsychiatrists to monitor children's developmental level and drug prescription when needed. All infants are also treated in Early Years Centers based in the community, where they receive individual unstructured interventions to foster children's development. Families allocated to the intervention group will also receive TAU.

Measures:

Baseline and sample descriptors:

Sociodemographic and child clinical variables will be collected from clinical notes and parent reports. Socioeconomic status will be determined using Hollingdale's Index of Social Position.

The following questionnaires will be administered:

- Social Communication Questionnaire (SCQ): it is a 40-item parent report measure, yes/no format, based on the Autism Diagnostic Interview-Revised (ADI-R). The Lifetime version of this questionnaire will be administered before the intervention to describe children's social communication difficulties. It is a robust tool that has shown good validity, and it has been widely adopted by both the research and clinical community.

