- Child Behavior Checklist (CBCL 1.5-5): this is a parent-reported 99-item inventory that addresses specific externalizing and internalizing behaviors. The sum of scores forms a total problem score, and it also includes scores for pervasive developmental problems and withdrawn subdomains. It will be collected before and after the intervention. It has shown good internal consistency, also in children with neurodevelopmental problems.
- Child Behavior Checklist (CBCL/6-18): it is a 113-item parent-response instrument that provides information about behavioral and emotional problems in children aged 6-18 years. It will be administered before the intervention to obtain information on social problems score and withdrawn-depressed score. It has shown good internal consistency.
- Vineland Adaptive Behavior Scale-III (VABS-III, parent/caregiver report form): it assesses adaptive functioning in different areas: communication (receptive, expressive, written), socialization (interpersonal/play and leisure time/coping), daily living skills (personal, domestic, community), and motor skills (fine and gross). It also generates a final adaptive composite score. This instrument will be used before the intervention to collect the level of functioning in different developmental areas. It has been considered a very efficient tool to measure the adaptive behavior profile of preschool children with developmental problems and shown excellent test-retest reliability.
- Developmental Profile-3 (DP-3): this is a 180-item parental questionnaire assessing developmental delays in different domains: motor, adaptive, socio-emotional, cognitive, and communication. It also computes an overall general development score. It will be used before the intervention to collect the child developmental level. It has shown good internal consistency.

- Autism Diagnostic Observation Schedule (ADOS-2): it is a semi-structured assessment of social interaction, communication and play exposing the child to situations that elicit spontaneous behaviors in standardized contexts. The Toddler Module will be used for children between 24 and 30 months, and Modules 1 to 3 will be selected in accordance to the children's language level. An experienced psychologist research assistant, trained to ADOS research standards, will conduct the assessment. To receive an autism or autism spectrum diagnosis by the ADOS-2 algorithm an individual's score must exceed a total cut-off score.

Outcomes:

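### Hypothesis VI covers children aged 3.0–7.11, but the CBCL/6-18, the form for those aged 6 and over, has no post-test scheduled

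*Protocol*

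**What the plan says.** Under Aims and Hypothesis, hypothesis VI expects parents in the intervention arm to report a fall in their children's "externalizing and internalizing symptoms when compared to the control group". It sets no age limit. The first inclusion criterion is "Children aged 3.0 – 7.11 years at recruitment".

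The inclusion criteria assign the CBCL form by age. The CBCL/1.5-5 serves children up to 5.11 years, and the other form is introduced by "For children over 6 years with social problems (defined as CBCL/6-18 scores above the borderline clinical range".

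Under Measures, Baseline and sample descriptors, the two forms are described next to each other:

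- CBCL 1.5-5, described as addressing externalizing and internalizing behaviours: "It will be collected before and after the intervention".
- CBCL/6-18, the parent-completed form for the older age group. Its timing and purpose are stated thus: "It will be administered before the intervention to obtain information on social problems score and withdrawn-depressed score".

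The effectiveness outcomes are parental stress (PSI-SF), parental depression (BDI), parenting practices (APQ-Pr), expressed emotion (five-minute speech sample) and interviews. The Data collection section says in general terms that data are gathered at baseline and again once the programme ends. It refers to children's outcome measures without naming an instrument.

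**The concern.** A between-arm effect on symptoms needs a symptom score after the intervention. The protocol plans one for the younger children and, on its wording, none for the older ones. If sites follow the instrument descriptions, children aged 6.0–7.11 will finish the trial with no post-intervention CBCL.

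The loss would be permanent once the post-test window has passed. The result for hypothesis VI would then describe only the younger children, while the hypothesis and the eligibility criteria invite a reading for the whole age range.

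**Working it through.** The point turns on the assessment schedule, so the first step is to compare how the protocol words the timing of each instrument.

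| Instrument | Section | Timing as worded |
|---|---|---|
| SCQ | Baseline and sample descriptors | Pre-intervention: "The Lifetime version of this questionnaire will be administered before the intervention to describe" |
| Vineland-III | Baseline and sample descriptors | Pre-intervention: "This instrument will be used before the intervention to collect the level of functioning in different developmental areas" |
| DP-3 | Baseline and sample descriptors | Pre-intervention |
| CBCL/6-18 | Baseline and sample descriptors | Pre-intervention: "It will be administered before the intervention to obtain information on social problems score and withdrawn-depressed score" |
| CBCL 1.5-5 | Baseline and sample descriptors | Pre and post: "It will be collected before and after the intervention" |
| PSI-SF, BDI, APQ-Pr, speech sample | Effectiveness outcomes | Pre and post |

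1. The wording separates two groups. Descriptors that are not repeated carry the pre-intervention phrase, and repeated measures carry the pre-and-post phrase. The CBCL/6-18 is worded like the first group, beside a sister form worded like the second.
2. The general sentence under Data collection does not change this. It names no instrument. Read as repeating everything, it would also repeat the SCQ, Vineland-III and DP-3, which are worded as pre-intervention only.
3. Nothing else supplies the missing score. No effectiveness outcome is a child symptom measure. The difficult-child domain of the PSI-SF is part of a parental stress scale. The interviews explore parents' perceived changes in their own skills and distress, and clinicians' experiences. No passage gives the CBCL 1.5-5 to children older than 5.11 years.

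**Number of children affected.** The planned size is 34 per arm, 68 in total. The 34 reproduces: a paired t test with d = 10/20 = 0.5, two-sided alpha 0.05 and power 80% gives n = 33.4, rounded up to 34. That calculation concerns the PSI-SF; 68 is used here only as a head count.

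The eligible span of 3.0–7.11 years is 60 months, of which 6.0–7.11 is 24 months. An even spread of ages gives 24/60 = 40% aged 6 or over. The protocol gives no age distribution, so a range is shown.

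| Assumed share aged 6 or over | Without post-test (68 × share) | Per arm (34 × share) | With post-test (68 − loss) |
|---|---|---|---|
| 20% | 13.6, about 14 | 6.8, about 7 | 54.4, about 54 |
| 40% | 27.2, about 27 | 13.6, about 14 | 40.8, about 41 |
| 50% | 34.0 | 17.0 | 34.0 |

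**The case against.** The best counter-argument is that the protocol never says the CBCL/6-18 is given only once. Its sentence sits under sample descriptors and may simply state the form's descriptive use. That section is also loosely drafted. It names a withdrawn-depressed score where the inclusion criterion for the same form uses thought problems, and it describes an ADOS module for children of 24 to 30 months although entry starts at 3.0 years. The Data collection section suggests that child outcomes are meant to be measured at both time points in everyone. So this may be a drafting slip and not a decision to omit the post-test.

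Some of this stands. The single administration is inferred from a consistent pattern of wording, and the sponsor may well intend a post-test. But a site works from the instrument descriptions, and these tell it to repeat one form and not the other. A general sentence that names no instrument does not override them.

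Two narrower points also stand. Naming only two scores for the CBCL/6-18 would not by itself lose data, because no reduced form is mentioned and other scores could be derived from the full baseline questionnaire; the missing post-test is what cannot be repaired. And the absence of a child symptom measure from the effectiveness outcomes concerns every age, so it shows only that nothing there fills the gap.

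**Conclusion.** The concern holds. As written, the assessment schedule does not support hypothesis VI in children aged 6.0–7.11. About 27 of 68 children would have no planned post-test symptom score under an even spread of ages, with a range of about 14 to 34 for shares of 20% to 50%. These counts rest on an assumed age mix; the mismatch between hypothesis and schedule does not.

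The matter cannot be left to a statistical analysis plan, which cannot analyse a questionnaire that was never given. The reach is limited to one secondary hypothesis in one age band of a feasibility trial. It should be corrected before post-test collection begins.

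**What to change.** The sponsor has two options.

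1. **Collect the data.** In the CBCL/6-18 description, schedule the form at both time points and name the externalizing and internalizing scores. List CBCL externalizing and internalizing scores among the secondary effectiveness outcomes. The cost is one further 113-item parent questionnaire at post-test for children aged 6 to 7, plus protocol wording. Because the two forms differ in length (99 and 113 items), the analysis plan must say how their scores are combined.
2. **Narrow the claim.** Restrict hypothesis VI and its conclusion to children assessed with the CBCL 1.5-5, and list that outcome among the effectiveness outcomes. This costs only wording, but the trial then gives no child symptom result for ages 6.0–7.11.

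The first option keeps the hypothesis as stated. If a post-test is already intended, correcting the timing and scores in the CBCL/6-18 description and adding the outcome to the list is enough.
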